1.4 Study purpose

The purpose of this Phase II study is to determine the efficacy of secukinumab in treating patients with a diagnosis of overuse, non-systemic inflammatory rotator cuff tendinopathy and to confirm the safety and tolerability profile of secukinumab in a dose of 300 mg s.c. given at day 1 and weekly until and including week 4, thereafter additional injections at weeks 8 and 12.

Commercially Confidential Information

. Patients will be followed up without treatment from week 12 to week 24 to investigate long-term safety.

2 Objectives and endpoints

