2.2 Secondary objective(s)

Objective	Endpoint

To assess the efficacy of secukinumab 300 mg s.c. vs. placebo in patients with overuse rotator cuff tendinopathy in relieving symptoms over time	
WORC score at Weeks 2, 4, 8, 12, 18 and 24Disability of Arm, Shoulder and Hand Questionnaire (QuickDASH) score at Weeks 2, 4, 8, 12, 14, 18 and 24American Shoulder and Elbow Surgeons Shoulder Evaluation Form (ASES) score at Weeks 2, 4, 8, 12, 14, 18 and 24EQ5D-5L score at Weeks 2, 4, 8, 12, 14, 18 and 24Pain score using a VAS scale (considering the last 24 hours) at Weeks 2, 4, 8, 12, 14, 18 and 24Patient global assessment (PGA) score using a VAS scale (considering the last 24 hours), at Weeks 2, 4, 8, 12, 14, 18 and 24Physician global assessment (PhGA) score using a VAS scale (considering the last 24 hours), at Weeks 2, 4, 8, 12, 14, 18 and 24

To assess the structural changes in the rotator cuff tendinopathy over time	
MRI Sein score at Weeks 8, 14 and 24

To assess PK/immunogenicity in secukinumab treated patients	
PK/immunogenicity assessment at Day 1, Weeks 4, 12, 24

To confirm the safety and tolerability of AIN457 in patients with overuse rotator cuff tendinopathy over time	
Safety and tolerability assessments over time: Incidence and severity of AEs and SAEs; routine safety laboratory parameters

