Furthermore, secukinumab 300 mg was more efficacious than 150 mg in achieving clinically meaningful improvements in skin disease, particularly with respect to clear/almost clear skin (PASI 90, IGA mod 2011 0/1) in patients with moderate to severe psoriasis (defined as $\geq 10\%$ BSA). There was a clear dose response favoring secukinumab 300 mg in the higher thresholds of skin clearance. The difference between 300 mg and 150 mg regimens was more pronounced in the more difficult-to-achieve PASI 90 and IGA mod 2011 0/1 endpoints, with 21.9% and 27.4% more patients with $\geq 10\%$ body surface area (BSA) compared to 8.2% and 3.3% more patients with $< 10\%$ BSA reaching PASI 90 and IGA mod 2011 0/1 responses, respectively, at Week 24. Therefore, secukinumab 300 mg afforded greater improvement in plaque psoriasis than 150 mg, particularly in the achievement of clear/almost clear skin, in patients with moderate to severe psoriasis ($\geq 10\%$ body surface area).

In addition, pertaining to safety assessment, there were no clinically meaningful differences among the secukinumab doses of 300 mg and 150 mg in the exposure adjusted incidences rates of the key risks over the entire treatment period in the 2 phase III trials in PsA patients. The overall safety in the PsA population was consistent with prior extensive experience in psoriasis, and showed that secukinumab 300 mg and 150 mg are acceptable for chronic use in adult patients with active PsA.

In study CAIN457F2312 the presence of enthesitis was assessed by using Leeds enthesitis score. Overall, the percentage of patients without resolution of enthesitis at Week 24 were 67.6%, 57.8% and 51.8% in the 75 mg, 150 mg and 300 mg s.c. groups, whereas it was 78.5% in the placebo group. At Week 24, these differences vs placebo were greater for the 150 mg and 300 mg dose groups vs placebo ($p=0.0108$ and $p=0.0025$, respectively), while 75 mg vs placebo was similar ($p=0.17$).

Treatment duration: The 12 weeks treatment duration was chosen as this is considered the maximum acceptable duration for resolution or partial resolution in subacute tendinopathy. The 12 weeks follow-up after the end of study treatment is included to generate follow-up data for potential relapse and to have treatment safety follow-up data in this indication.

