³ Serum pregnancy test required as Screening and EOS, for remaining visits: urine test

⁴ At study days 8 and 22 study medication can be administered by study nurse at patients home

⁵ Collected pre-dose if applicable

⁶ Historic data accepted if obtained ≤3 months before baseline

⁷ A chest X-ray (can be replaced by historic CT or MRI) is required if it was not performed and evaluated within 3 months prior to screening. The X-ray should be performed after it is certain the subject meets other inclusion/exclusion criteria in order to minimize unnecessary exposure to radiation.

⁸ To be done the night before and the night after each visit (except for EOS when it is done only before the visit).

⁹ Commercially Confidential Information

¹⁰

¹¹ The PPD skin test can be performed at any time during the screening period, but it must be read within 72 hours and before randomization

¹² Assessments to be performed maximum 14 days before study Day 1

¹³ Duration of the standardized physiotherapy might be prolonged if required by local regulations

S: collected as source data only

For all subjects who discontinue from the study, the investigator should ensure that the subject completes the end of treatment visit (EOS) 4 weeks after last study treatment of secukinumab. Every attempt should be made to obtain MRI images at the final visit, unless the MRI was taken within 8 weeks before discontinuation.

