11.4.4 Summary statistics of safety

Vital signs

All vital signs data will be listed by treatment group, subject, and visit/time and if ranges are available abnormalities (and relevant orthostatic changes) will be flagged. Summary statistics will be provided by treatment and visit/time.

Clinical laboratory evaluations

All laboratory data will be listed by treatment group, subject, and visit/time and if normal ranges are available abnormalities will be flagged. Summary statistics will be provided by treatment and visit/time.

Adverse events

All information obtained on adverse events will be displayed by treatment group and subject.

The number and percentage of subjects with adverse events will be tabulated by body system and preferred term with a breakdown by treatment. A subject with multiple adverse events within a body system is only counted once towards the total of this body system.

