7.2 Descriptive analyses

Patient demographics and other baseline characteristics

All data for background and demographic variables will be listed by treatment group and patient. Summary statistics will be provided by treatment group.

Relevant medical history, current medical conditions, results of laboratory screens, drug tests and any other relevant information will be listed by treatment group and patient.

Treatment

Data for study drug administration and concomitant therapies (including rescue medication) will be listed by treatment group and patient.

Vital signs

All vital signs data will be listed by treatment, patient, and visit/time and if ranges are available abnormalities (and relevant orthostatic changes) will be flagged. Summary statistics will be provided by treatment and visit/time.

ECG evaluations

All ECG data will be listed by treatment, patient and visit/time, abnormalities will be flagged. Summary statistics will be provided by treatment and visit/time.

Clinical laboratory evaluations

All laboratory data will be listed by treatment, patient, and visit/time and if normal ranges are available abnormalities will be flagged. A separate listing is provided presenting all parameters in a patient with any abnormal values. Summary statistics will be provided by treatment and visit/time.

Serum chemistries will include sodium, potassium, BUN/urea, bicarbonate, calcium, phosphorous, total protein, calcium, albumin, uric acid, creatinine, CK, total bilirubin, AST (SGOT), ALT (SGPT), GGT and alkaline phosphatase, at all timepoints specified in the Assessment schedule.

If the total bilirubin concentration is increased above 1.5 times the upper limit of normal, direct and indirect reacting bilirubin should be differentiated.

Triiodothyronine (T3), thyroxine (T4), thyroid-stimulating hormone (TSH), Rheumatoid factor (RF), anti-cyclic citrullinated peptide (anti-CCP) antibodies, and interferon-gamma release test done only at screening. FSH is only done at screening and only in patients who are reported post-menopausal at screening.

Adverse events

All information obtained on adverse events will be displayed by treatment group and patient. The number and percentage of patient s with adverse events will be tabulated by body system and preferred term with a breakdown by treatment. A patient with multiple adverse events within a body system is only counted once towards the total of this body system.

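### Follow-up to Week 24 is justified by long-term safety, but no visible adverse event summary separates follow-up from dosing or allows for unequal observation time

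*Protocol*

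**What the plan says.** Protocol 1.4 states the purpose of the second half of the study: "Patients will be followed up without treatment from week 12 to week 24 to investigate long-term safety". Section 3.3 repeats it, alongside relapse, as the wish "to have treatment safety follow-up data in this indication". The matching secondary endpoint in section 2.2 is "Safety and tolerability assessments over time: Incidence and severity of AEs and SAEs; routine safety laboratory parameters".

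The planned AE analysis in protocol 11.4.4, repeated in 11.5.2, is: "The number and percentage of subjects with adverse events will be tabulated by body system and preferred term with a breakdown by treatment". SAP 7.2 keeps the same rule: patients "with adverse events will be tabulated by body system and preferred term with a breakdown by treatment". The denominator is the safety set, which is everyone who received any study drug (protocol 11.1, SAP section 4). Neither text mentions period, visit or person-time for AEs. In the same sections, vital signs and laboratory data are summarised by treatment and visit, and the SAP adds ECG.

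SAP 7.2 also plans two disclosure tables of treatment-emergent events, one non-serious and one serious. They are broken down by arm only, and neither document says when the treatment-emergent window starts or ends.

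On how long patients are observed:
- AEs are recorded from consent until the end-of-study visit (protocol 8.4 and 9.1).
- For patients who discontinue, the text below Table 8-1 asks that the subject "completes the end of treatment visit (EOS) 4 weeks after last study treatment of secukinumab".
- Protocol 7.2 instead asks for that visit as soon as possible after stopping. It adds that such patients are not withdrawn unless they withdraw consent, and that those who miss the visit should be contacted, preferably on the visit schedule.
- Protocol 9.2.2 takes SAE reporting to the last day of study, described as 12 weeks after the last dose.

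**The concern.** Two separate things are lost in a single percentage per arm.

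First, the question that follow-up is meant to answer. The last dose is at Week 12, so half of the 24-week window is free of treatment. After Week 14 a steroid injection and NSAID changes are also permitted (protocol 3.2, 3.5, 6.9). A table over the whole study cannot show whether an event arose under study drug or after it, and a difference confined to one period is diluted by the other.

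Second, comparability of observation. A completer is watched for 24 weeks. A patient who stops early may be watched for far less, yet carries the same weight in the denominator. For efficacy, the SAP restricts the Day 127 and Day 169 analyses to patients who completed the relevant epochs; safety has no counterpart. If early stopping differs between arms for reasons unrelated to AEs, the arm with more stopping shows a lower percentage merely because it was observed for less time.

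**Working it through.** The documents contain no AE figure to reproduce. The nearest is the sample size: about 50 patients per arm (protocol 6.2) and 40 per group completing Week 14 (11.7), which leaves room for 1 − 40/50 = 20% non-completion per arm. Everything below is illustration under stated assumptions.

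**1. Observation time.** Planned person-time per arm is 50 × 24 = 1200 weeks. Assume 10 early stoppers with a last dose at Week 0, 4 or 8 and observation ending 4 weeks later:
- end at Week 4: 40 × 24 + 10 × 4 = 1000 weeks (83%)
- end at Week 8: 40 × 24 + 10 × 8 = 1040 weeks (87%)
- end at Week 12: 40 × 24 + 10 × 12 = 1080 weeks (90%)

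So 10% to 17% of planned person-time is unobserved while all 50 patients stay in the denominator.

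**2. Unequal stopping, no true difference.** Assume the same constant hazard in both arms, stopping unrelated to AEs, last doses spread evenly over Day 1 and Weeks 1, 2, 3, 4 and 8, and the 4-week rule below Table 8-1. Stoppers are then observed for 4, 5, 6, 7, 8 or 12 weeks (mean 42/6 = 7). For 24-week risk R and stopping fraction d:
- hazard h = −ln(1 − R)/24 per week
- stopper risk s = mean of 1 − exp(−h × t) over the six values of t
- crude percentage = (1 − d) × R + d × s

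For R = 50%, h = 0.0289 and s = 18.1%:
- d = 10%: 0.9 × 50 + 0.1 × 18.1 = 46.8%
- d = 20%: 0.8 × 50 + 0.2 × 18.1 = 43.6%
- d = 30%: 0.7 × 50 + 0.3 × 18.1 = 40.4%

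The false difference is (difference in d) × (R − s):

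| R | s | 10% vs 20% stopping | 10% vs 30% stopping |
|---|---|---|---|
| 30% | 9.8% | 2.0 points | 4.0 points |
| 50% | 18.1% | 3.2 points | 6.4 points |
| 70% | 29.0% | 4.1 points | 8.2 points |

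With equal d in both arms the false difference is zero in this model.

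**3. Merged periods, no stopping at all.** Assume two 12-week periods and a raised risk on secukinumab only while dosed, with both arms at the placebo risk afterwards. The 24-week risk is 1 − (1 − dosing risk) × (1 − follow-up risk).
- Dosing 20% vs 10%, follow-up 10% in both: 1 − 0.8 × 0.9 = 28.0% vs 1 − 0.9 × 0.9 = 19.0%. The risk ratio falls from 2.00 to 1.47.
- Dosing 35% vs 20%, follow-up 20%: 48.0% vs 36.0%; from 1.75 to 1.33.
- Dosing 45% vs 30%, follow-up 30%: 61.5% vs 51.0%; from 1.50 to 1.21.

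This loss of contrast does not depend on anyone stopping early.

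**The case against.** The case for leaving the plan alone has real weight.

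- Crude incidence with patient listings is a usual description for a fixed-duration Phase II trial of about 100 patients whose safety analysis is descriptive. At R = 50% and 50 per arm, the standard error of the difference is √(2 × 0.25/50) = 10 points, so a 3.2-point distortion is about a third of it. This limits the importance of the point but supplies no follow-up summary.
- The stopping imbalance is assumed. The protocol figures imply up to 20% non-completion per arm and nothing about a difference. This stands.
- A reader might infer that the crude table flatters the less well tolerated arm. The documents do not support that. A patient who stops because of an AE is already in the numerator. If every stopper had an event and completers had 50%, the crude figure would be 0.9 × 50 + 10 = 55% with 10% stoppers and 0.7 × 50 + 30 = 65% with 30%, which counts against the arm with more stopping.
- A reader might infer that stoppers are observed for only 4 weeks after the last dose. That is one of several conflicting rules; if contact continues on the visit schedule, the shortfall shrinks.
- A reader might infer that follow-up safety goes unanalysed. Laboratory, vital sign and ECG data are summarised by visit, so neutropenia, for example, is partly covered. The gap concerns AEs and SAEs.
- A reader might infer that no Week 14 safety cut exists. The SAP sections on first interpretable results and interim analyses are redacted and may contain one.
- Protocol 3.3 compares doses in psoriatic arthritis "in the exposure adjusted incidences rates of the key risks over the entire treatment period". That shows the sponsor uses the metric. It does not establish that the crude table cannot be compared with the sponsor's other safety data, since section 1.3.1 is redacted.

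**Conclusion.** The point holds in a limited form. The treatment-free period and the endpoint over time have no matching AE summary in the visible text, and nothing visible adjusts for shorter observation of early stoppers. The treatment-emergent tables cannot be credited with closing the gap while their window is undefined; equally, it cannot be shown that they merge the periods.

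The between-arm distortion is about 2 to 8 points under 24-week risks of 30% to 70%, a constant equal hazard, 10% versus 20% to 30% stopping unrelated to AEs, and the 4-week rule. It is small if stopping is balanced, and its direction is not predictable in general because AE-driven stoppers are already counted. The dilution from merging periods needs no stopping but does assume a risk that differs by period. This is a worthwhile improvement to the safety reporting, not a flaw that invalidates it.

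**What to change.** In SAP 7.2 and protocol 11.5.2:

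1. Keep the crude table as planned.
2. Define treatment emergent with a start and an end. The start should be first dose, because AEs are recorded from consent and pre-dose events could otherwise enter the tables.
3. Add the AE and SAE table split into first dose to the Week 14 visit, and after the Week 14 visit to end of study, with the patients entering each period as denominator.
4. Add exposure-adjusted incidence by arm (patients with at least one event per 100 patient-years at risk) for all AEs, SAEs and the risks named in protocol 3.7, and a table of observation time by arm. Because such a rate assumes a roughly constant hazard, read it together with the period split.
5. Reconcile the statements on follow-up of early stoppers in protocol 7.2, below Table 8-1 in 8.1, and in 9.2.2, so that the end of observation is defined.

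The cost is SAP wording and a few extra tables; AE start and end dates are already collected (protocol 9.1). The drawback is that the Week 14 boundary is a convention, since drug persists after the last dose, and the tables should say so.

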2.1 Primary objective(s)

Objective	Endpoint

To assess the efficacy of secukinumab 300 mg s.c. vs. placebo in patients with overuse rotator cuff tendinopathy in relieving clinical symptoms at week 14	
The Western Ontario Rotator Cuff (WORC) patient reported outcome (PRO) score at week 14

2.2 Secondary objective(s)

Objective	Endpoint

To assess the efficacy of secukinumab 300 mg s.c. vs. placebo in patients with overuse rotator cuff tendinopathy in relieving symptoms over time	
WORC score at Weeks 2, 4, 8, 12, 18 and 24Disability of Arm, Shoulder and Hand Questionnaire (QuickDASH) score at Weeks 2, 4, 8, 12, 14, 18 and 24American Shoulder and Elbow Surgeons Shoulder Evaluation Form (ASES) score at Weeks 2, 4, 8, 12, 14, 18 and 24EQ5D-5L score at Weeks 2, 4, 8, 12, 14, 18 and 24Pain score using a VAS scale (considering the last 24 hours) at Weeks 2, 4, 8, 12, 14, 18 and 24Patient global assessment (PGA) score using a VAS scale (considering the last 24 hours), at Weeks 2, 4, 8, 12, 14, 18 and 24Physician global assessment (PhGA) score using a VAS scale (considering the last 24 hours), at Weeks 2, 4, 8, 12, 14, 18 and 24

To assess the structural changes in the rotator cuff tendinopathy over time	
MRI Sein score at Weeks 8, 14 and 24

To assess PK/immunogenicity in secukinumab treated patients	
PK/immunogenicity assessment at Day 1, Weeks 4, 12, 24

To confirm the safety and tolerability of AIN457 in patients with overuse rotator cuff tendinopathy over time	
Safety and tolerability assessments over time: Incidence and severity of AEs and SAEs; routine safety laboratory parameters

2.3 Exploratory objective(s)

Commercially Confidential Information

Commercially Confidential Information

3 Investigational plan

3.1 Study design

This is a randomized, double-blind, placebo-controlled, multi-center, Phase II study of s.c. secukinumab 300 mg in approximately 100 randomized patients with overuse rotator-cuff tendinopathy without systemic inflammatory disease and refractory to NSAIDs/acetaminophen, physiotherapy or corticosteroids. The patient and investigator will be blinded throughout the study, while the sponsor will be blinded until after the analysis of the primary endpoint. The study consists of a 4-week screening period, a 2-week run-in period, a 12-week treatment period and a 12-week follow-up period after last treatment ([Figure 3-1](#)).

The population will consist of patients with MRI-positive unilateral overuse (non-systemic inflammatory) shoulder tendinopathy, 18 - 65 years of age. Symptoms should have been present for at least 6 weeks but not more than 12 months. The tendinopathy must have been refractory to NSAIDS/acetaminophen as defined in the inclusion criteria. On MRI, patients may have no tendon tear or a partial tendon tear (up to 50% thickness, in max. 50% of patients). The patients should also have had at least 2 weeks of a standardized physiotherapy treatment.

[figure not shown]
The screening period will be used to assess eligibility and to start/continue patients on physiotherapy. In the run-in period the patient should have 2 weeks of stable NSAID/acetaminophen intake and standardized physiotherapy (defined in the SOM). Patients who meet the eligibility criteria at screening after the run-in period will go through baseline evaluations.

Eligible subjects as per inclusion/exclusion criteria will be randomized to one of the two treatment arms: 7 s.c. injections of secukinumab 300 mg or placebo in a 12-week treatment period, followed by a 12-week follow-up period. Randomization will be stratified by the following 2 factors: Partial tear/no tear and previous steroid injection (yes/no), in order to achieve approximate balance between these factors in the treatment groups. The assessments to address the primary endpoint will be performed at 14 weeks (2 weeks after the last injection).

Patients will come to the out-patient clinic approximately 2-4 hours prior to dosing for the evaluations. Dosing will be on-site, except for injections at 1 and 3 weeks, that can be done either on site or by a nurse at the patient's home.

Safety assessments will include physical examinations, ECGs, vital signs, standard clinical laboratory evaluations (hematology, blood chemistry, and urinalysis), adverse event and serious adverse event monitoring.

Figure 3-1 Study design

3.2 Rationale for study design

The study design addresses the primary objective of determining the efficacy of secukinumab in improving signs, symptoms and structure in patients with overuse rotator cuff tendinopathy. The study will enroll patients with inadequate response (determined by a VAS pain score ≥ 4) to physiotherapy or NSAIDs/acetaminophen or intolerance to NSAIDs/acetaminophen, using a double-blinded, randomized, parallel group design to minimize bias. At the time of inclusion, patients can be steroid-naïve or have inadequate response or intolerance to local steroid injection in the tendon, but last steroid therapy must have been >8 weeks prior to randomization. Patients must be naïve to IL-17 inhibition therapy.

The patient population with rotator cuff tendinopathy was chosen, as this is one of the most frequent tendinopathies. Moreover, the clinical evidence for an IL-17 connection has so far only been shown for rotator cuff tendinopathy and has not been investigated for other tendinopathies (Millar et al 2017).

Currently, no Health Authority guideline exists for developing drugs for the overuse tendinopathy indication. The 14-week endpoint is chosen to allow the last injection at 12 weeks to take effect.

The study uses validated Patient Reported Outcome (PRO) questionnaires including indices of signs, symptoms and physical function. The PROs used have been chosen based on their validity, reliability and specificity. The different PROs have different recall times, 1 week, 24 hours, and a moment in time. One is specific for rotator cuff; two others are for arm and shoulder.

During the 2-week run-in period patients should take NSAIDs/acetaminophen at a stable and adequate (or maximally tolerable) dose, and still have inadequate control of symptoms at randomization. Alternatively NSAID should have been stopped due to intolerance. Patients who tolerate it will continue taking the NSAID regimen from the run-in period. Patients should not increase the NSAID/acetaminophen dose, but can choose to decrease the dose at any time. Dose adjustments are allowed after the primary endpoint at 14 weeks. During first 14 weeks of the study local steroid injection is not allowed. After assessment of the primary endpoint at week 14 patients may have 1 steroid injection during the last 10 weeks observation period. The stable NSAID dosing and avoidance of steroid injections are required in order not to have other variables than AIN457 influencing the effect on the tendinopathy.

The rationale for key design elements in this study include:

Randomization: This decreases the chance of an imbalance in subject characteristics between groups, thereby facilitating a valid basis for the treatment comparison.

Double-blind: Blinding of subjects, investigators and sponsor up to the point of week 14, the primary endpoint, allows for an unbiased assessment of subjective readouts such as the efficacy parameters, especially the PROs and as well for adverse events evaluation. The blinding is maintained for patient and investigator beyond the primary endpoint until the end of the study to ensure reliable efficacy and safety measures. The sponsor will be unblinded after the primary endpoint analysis.

Placebo-controlled: A placebo arm is included in this study because it is not known whether secukinumab can improve tendinopathy, and because there is no disease modifying therapy available. However, standard of care with NSAIDs and physiotherapy will be given to both treatment groups throughout the study, and if required a steroid injected into the tendon can be given also in both groups. Due to the nature of the disease and the outcome measures used, a placebo arm is necessary to obtain reliable efficacy measurements, to judge the size of the active treatment compared to change over time in the placebo group, and to reasonably attribute adverse events to secukinumab.

